#### ***12.4.4 Demographics and Baseline Characteristics***

Demographic and baseline characteristics will be summarized descriptively.

#### ***12.4.5 Extent of Study Treatment Exposure and Compliance***

The extent of study treatment exposure and compliance will be assessed and summarized by actual treatment received within the safety population.

The duration of study drug exposure is defined as last dose date – first dose date + 1 day, regardless of intermittent discontinuations.

A given administration will be considered noncompliant if the participant did not take the planned dose of treatment as required by the protocol. No imputation will be performed for participants with missing or incomplete data.

Treatment compliance, above-planned and under-planned dosing percentages will be summarized descriptively (number [n], mean, SD, median, minimum, and maximum). The participants with compliance <80% will be fully described and summarized. In addition, number and percentage of participants with at least 1 dosing administration will be given, as well as the number and percentage of participants with 0, (0, 20%), and >20% under-planned dosing administrations.

#### **12.4.6        *Efficacy Analyses***

All efficacy analyses will be performed on the ITT population, with sensitivity analysis also performed on the Per Protocol Population.

##### **12.4.6.1        Primary Efficacy Endpoint Analyses**

The primary efficacy endpoints of clinical response will be analyzed using the Cochran-Mantel-Haenszel (CMH) test for stratified categorical data. Early dropouts or participants whose response status is unable to be assessed at the end of 30-week dosing period will be classified as non-responders. More detailed statistical analysis strategies will be documented in the SAP.

##### **12.4.6.2        Secondary Efficacy Endpoints Analyses**

The general analytical approach for the secondary efficacy endpoints are as follows:

- To minimize false discovery among the secondary endpoints appropriate methods will be employed to control the familywise Type 1 error. Further details will be specified in the SAP.
- Categorical endpoints will be analyzed by comparing the respective proportions of the 2 treatment groups using CMH tests with adjusting for stratification factors, or Chi-square tests without adjusting for stratification factors, whenever appropriate.
- Continuous variables will be analyzed by analysis of variance (ANOVA) evaluating the treatment group differences against the null of zero difference.
- Ordinal variables, such as NYHA functional class, will be converted quantitatively as ordinal scores (I-IV classes to 1-4 scores, respectively) and analyzed as continuous variables.

Specific details will be provided in the SAP.

A series of black redaction bars of varying lengths and positions, appearing to be a scan of a document with sensitive information removed.

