Sample Size and Statistical Considerations	Approximately 220 participants will be randomized, with 110 participants in each of the 2 groups. Randomization will be stratified for NYHA functional class, current treatment with $\beta$ -blocker, type of ergometer, and consent for the CMR substudy. The sample size should provide adequate power to determine the superiority of mavacamten in improving pVO 2 and NYHA functional classification relative to placebo. The power calculation is derived assuming a true clinically meaningful difference of 25% between mavacamten and placebo subjects in achieving the clinical response. Based on the MYK-461-004, PIONEER-HCM phase 2 study, 50% of the subjects receiving mavacamten met the clinical responder definition by the end of 12-week treatment period. Assuming the same percentage of subjects in the active treatment arm and 25% in placebo arm will achieve the clinical response at the end of 30-week dosing period in the current study, the proposed sample size of 110 subjects per arm will provide 96% power at two-sided 5% statistical significance level. Subjects who terminate early or cannot be assessed for the clinical response at the end of 30-week dosing period will be considered as non-responders.
	Efficacy Analyses Primary efficacy endpoints analysis The primary efficacy endpoints of clinical response will be analyzed using the Cochran-Mantel-Haenszel test for stratified categorical data. Early dropouts or participants whose response status is unable to be assessed at the end of 30-week dosing period will be classified as non-responders. More detailed statistical analysis strategies will be documented in the Statistical Analysis Plan (SAP). Secondary efficacy endpoints analyses The general analytical approach for the secondary efficacy endpoints are the following: 

• To minimize false discovery among the secondary endpoints, appropriate methods to control Type 1 errors will be employed; further details will be specified in the SAP.

• Categorical endpoints will be analyzed by the Cochran-Mantel-Haenszel test taking into account of stratification factors or Chi-square test without adjusting for stratification factors, whenever appropriate.

• Continuous variables will be analyzed by analysis of variance (ANOVA) model comparing between group means.

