## 12.4 Statistical Analysis

Before database lock, final SAPs for clinical data and PK data will be prepared that contain full details of all planned analyses. The analyses presented here represent an outline of the intended methodology.

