6.4. Missing Data

In general, missing data will not be imputed unless specifically stated in this SAP. For mixed-model repeated-measure analyses, missing data are handled implicitly by the model. For the responder analysis of primary and secondary endpoints, refer [Section 8.1](#) and [8.2](#) for the specific handling rules.

Handling of Missing Data:

- For values below the lower limit of quantitation (LLOQ), 1/2 LLOQ will be imputed unless otherwise specified.
- For values above the upper limit of quantitation (ULOQ), ULOQ + 1 unit of significant digit will be imputed unless otherwise specified.
- In general, for missing or partial dates the following is noted:
 - Start Dates:
 - If day is missing, then impute it to be the start of the month (eg, 01 MMM YYYY); except if the month and year is equal to the first dose date month and year then impute the day to be the same day as the first dose date.
 - If month is missing, then impute it to be the start of the year (eg, 01 JAN YYYY), except if the year is equal to the first dose date year then impute the day and month to be the same as the first dose date.
 - If year is missing, then do not impute.
 - End Dates:
 - If day is missing, then impute it to be the end of the month (eg, 31 MMM YYYY), except if the month and year is equal to the last

assessment date month and year then the day should be imputed to the last assessment date day.

- If month is missing, then impute it to be the end of the year (eg, 31DECYYYY), except if the year is equal to the last assessment date year then the day and month should be imputed to the last assessment date day and month.
- If year is missing then do not impute.
- For all other type of dates:
 - If only day is missing, then impute it to be the start of the month (eg, 01MMMYYYY).
 - If month and day are missing, then impute it to be the start of the year (eg, 01JANYYYY).
 - If year is missing, then do not impute.

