APPENDIX 2.

Table 5: Analysis Window Definition for NYHA class and NT-proBNP

Analysis Visit	Analysis Visit Window	Analysis Visit Target Day
Baseline	Screening <= analysis day <=1	1
Week 4	15 < analysis day <= 36	29
Week 6	36 < analysis day <= 50	43
Week 8	50 < analysis day <= 71	57
Week 12	71 < analysis day <= 92	85
Week 14	92 < analysis day <=113	99
Week 18	113< analysis day <=141	127
Week 22	141< analysis day <=169	155
Week 26	169<analysis day <=197	183
Week 30	197<analysis day <=239	211
Week 38	239<analysis day <=295	267

Table 6: Analysis Window Definition for CPET, Stress Echo and CMR Measurements

Analysis Visit	Analysis Visit Window	Analysis Visit Target Day
Baseline	Screening <= analysis day <=1	1
Week 30	183 < analysis day <= 239	211

Table 7: Analysis Window Definition for Resting TTE

Analysis Visit	Analysis Visit Window	Analysis Visit Target Day
Baseline	Screening <= analysis day <=1	1
Week 4	15 < analysis day <= 36	29
Week 6	36 < analysis day <= 57	43
Week 12	71 < analysis day <= 99	85
Week 18	113< analysis day <=141	127
Week 22	141< analysis day <=169	155
Week 26	169<analysis day <=197	183
Week 30	197<analysis day <=239	211
Week 38	239<analysis day <=295	267

Table 8: Analysis Window Definition for hs-Cardiac Troponin I

Analysis Visit	Analysis Visit Window	Analysis Visit Target Day
Baseline	Screening <= analysis day <=1	1
Week 6	29 < analysis day <=57	43
Week 18	113<analysis day <=141	127
Week 30	197 < analysis day<=239	211
Week 38	239<analysis day<=295	267

Table 9: Analysis Window Definition for PGIS and PGIC

Analysis Visit	Analysis Visit Window	Analysis Visit Target Day
Baseline	Screening <= analysis day <=1	1
Week 6	29 < analysis day <= 57	43
Week 10	57 < analysis day <= 85	71
Week 14	85 < analysis day <=113	99
Week 18	113<analysis day <=141	127
Week 22	141< analysis day <=169	155
Week 26	169<analysis day <=197	183
Week 30	197<analysis day <=239	211
Week 38	239<analysis day <=295	267

Table 10: Analysis Window Definition for WPAI-SHP, EQ-5D-5L, and KCCQ-23

Analysis Visit	Analysis Visit Window	Analysis Visit Target Day
Baseline	Screening <= analysis day <=1	1
Week 6	29 < analysis day <= 57	43
Week 12	71 < analysis day <= 99	85
Week 18	113< analysis day <=155	127
Week 30	197<analysis day <=239	211
Week 38	239<analysis day <=295	267

Table 11: Analysis Window Definition for HCMSQ

Analysis Visit	Analysis Visit Window	Analysis Visit Target Day
Baseline	Screening <= analysis day <= 1	1
Week 4	15 <= analysis day < 36	29

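### For post-exercise LVOT gradient and pVO2, baseline-adjusted ANCOVA would be an optional, near-costless gain in precision over the ANOVA outlined in the protocol; the SAP model is redacted and may already adjust

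*Protocol*

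**What the plan says.** Protocol Section 12.4.6.2 gives one line for all continuous secondary endpoints: "Continuous variables will be analyzed by analysis of variance (ANOVA) evaluating the treatment group differences against the null of zero difference". The Synopsis has the parallel line: "Continuous variables will be analyzed by analysis of variance (ANOVA) model comparing between group means". Neither names a covariate, and neither rules one out. In the same list in Section 12.4.6.2, the item on categorical endpoints does provide for CMH tests adjusted for the stratification factors. The item on continuous endpoints has no counterpart. Randomisation uses four binary factors: NYHA class, beta-blocker use, ergometer type and consent to the CMR substudy (Protocol 6.1, SAP 4.1).

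The protocol limits the weight of these lines. Section 12.4 says: "The analyses presented here represent an outline of the intended methodology". Section 12.4.6.2 adds: "Specific details will be provided in the SAP".

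The visible SAP text runs from Section 7.4 to Section 10, and what lies between is blacked out, including Sections 8.1 and 8.2, to which SAP 6.4 refers. SAP 6.4 also says: "For mixed-model repeated-measure analyses, missing data are handled implicitly by the model". It does not say which endpoints those models serve. SAP Section 14 is the place for changes to the protocol's analyses, but its content cannot be seen.

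In SAP Appendix 2, "Table 6: Analysis Window Definition for CPET, Stress Echo and CMR Measurements" contains a baseline window and one post-baseline window, Week 30. Table 10 gives KCCQ-23 five post-baseline windows (Weeks 6, 12, 18, 30, 38), and Table 11 gives the HCMSQ nine (Weeks 4, 6, 10, 14, 18, 22, 26, 30, 38).

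**The concern.** Both endpoints are changes from baseline with a measured baseline. Comparing raw mean changes fixes the coefficient on baseline at 1. ANCOVA estimates that coefficient, and so usually gives a smaller standard error for the same treatment effect. If any stratification factor is prognostic, leaving it out after stratified randomisation also tends to overstate the standard error.

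Post-exercise LVOT gradient and pVO2 are steps 1 and 2 of the fixed sequence in SAP 6.5. A non-significant result at either step bars every later claim, including both patient-reported outcomes. Precision is therefore worth most at these two steps, if it can be had cheaply.

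The point is confined to these two endpoints. With a single post-baseline window, the SAP's remark on repeated-measures models does not settle how they are analysed. KCCQ and HCMSQ have several windows and may well fall under such a model.

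**Working it through.** **The plan's own figure.** The only power figure in the documents is 96% for the primary responder endpoint: 50% versus 25%, 110 per arm, two-sided 5% (Protocol 12.1). Unpooled check: SE = √[(0.25 + 0.1875)/110] = 0.0631; 0.25/0.0631 − 1.96 = 2.00; power 97.7%. The pooled version gives 97.4%. With a continuity correction, 96% power needs 108 per arm, so the stated figure is reproduced. It says nothing about the continuous endpoints, for which no power, SD or correlation is given.

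**Inputs.** N = 220 (Protocol 12.1). Covariates: baseline plus four binary factors, q = 5. Assumed, because the documents are silent: the baseline-to-Week 30 correlation r, and k = SD at Week 30 / SD at baseline, both taken as the same in each arm.

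**Gross variance ratio, ANCOVA to ANOVA on change:**

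k²(1 − r²) / (1 + k² − 2rk)

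With k = 1 this is (1 + r)/2. Denominator minus numerator equals (1 − rk)², which is never negative. Before the covariate cost, ANCOVA therefore cannot be less precise than the change score.

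**Expected covariate cost** if the covariates explain nothing: 1 + q/(N − q − 3).
- Baseline alone: 1 + 1/216 = 1.0046, about 0.5%.
- Baseline plus four factors: 1 + 5/212 = 1.0236, about 2.4%. This is the most that can be lost in expectation.

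**Net ratio** = gross × cost, with the factors assumed to have no prognostic value:

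| r | gross, k = 1 | baseline only, k = 1 | five covariates, k = 1 | five, k = 0.85 | five, k = 1.15 |
|---|---|---|---|---|---|
| 0.3 | 0.650 | 0.653 | 0.665 | 0.555 | 0.755 |
| 0.5 | 0.750 | 0.753 | 0.768 | 0.636 | 0.866 |
| 0.7 | 0.850 | 0.854 | 0.870 | 0.708 | 0.969 |
| 0.9 | 0.950 | 0.954 | 0.972 | 0.730 | 1.019 |

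Worked cell, k = 1.15 and r = 0.9: 1.3225 × 0.19 / (1 + 1.3225 − 2.07) = 0.2513/0.2525 = 0.995; × 1.0236 = 1.019, a 2% increase.

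**Break-even at k = 1:** 2/1.0236 − 1 = 0.954 with five covariates; 2/1.0046 − 1 = 0.991 with baseline alone.

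**Simulation checks.** With 20,000 trials per r, 110 per arm, factors without effect and k = 1, the ratios were 0.671, 0.762, 0.874 and 0.966 at the four values of r, and 1.000 at r = 0.95. A separate simulation with stratified allocation (6,000 trials per setting) gave 0.654, 0.756, 0.850 and 0.955. Its null rejection rates were 0.048 to 0.056 for ANCOVA and 0.046 to 0.059 for ANOVA, so the type I error is kept either way.

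**What this means for power, on an assumed reference.** If unadjusted ANOVA had 80% power, net power would be Φ(2.802/√ratio − 1.960): 93.0%, 89.2%, 85.2% and 81.1% for the five-covariate, k = 1 column. The 80% is a yardstick, not a figure from the plan.

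**The case against.** The best case against raising the point is that it may have no target. The protocol text is an outline, the operative model belongs in a redacted SAP section, and redacted text is not missing from the plan. The reference to mixed models, which the protocol's list of methods does not mention, shows that the SAP has already moved beyond that list. This stands, and it rules out calling the matter a defect.

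Second, ANOVA in the protocol need not mean one-way. A model with the four factors would fit the same sentence, and the comparison above takes the least favourable reading. This also stands, but it changes little. Adding baseline to such a model costs 213/212, again about 0.5%, and the gain from baseline is close to the baseline-only column.

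Third, the size of the gain is unknown. Over the assumed ranges, the five-covariate result runs from a 45% variance reduction to a 2% increase. True, which is why the range is shown. What does not depend on r or k is that the expected loss cannot exceed the covariate cost.

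Fourth, writing a specific model into the protocol before SAP 8.2 has been read could create a mismatch. This is right, and it sets the order of the fix.

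A reader might infer that the trial will analyse these endpoints without adjustment, or that the later steps of the sequence are at risk. The documents support neither: the final model is not visible, and nothing shows marginal power at step 1 or 2.

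**Conclusion.** The point holds as an optional, minor improvement in precision. The protocol's visible text names ANOVA without listed covariates. For post-exercise LVOT gradient and pVO2, ANCOVA would probably do better at almost no cost.

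With equal SDs and five covariates, the gain is substantial at low or middle correlation and small at r = 0.9. A smaller Week 30 SD (k = 0.85) raises the net reduction to between 45% and 27%. A larger one (k = 1.15) lowers it to between 25% and slightly below zero. These sizes rest on assumed r and k, and on factors without prognostic value. The factors add precision only if they are prognostic; the baseline value does most of the work.

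This is not a question of validity: unadjusted ANOVA remains valid under randomisation. The primary endpoint and its power are untouched. Nor does the point extend to KCCQ or HCMSQ.

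**What to change.** Before unblinding, read SAP Section 8.2 for these two endpoints.

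- **If it uses unadjusted ANOVA**, replace it with: *Post-exercise LVOT peak gradient and pVO2: ANCOVA of change from baseline to Week 30, with terms for treatment, baseline value, NYHA class, beta-blocker use, ergometer type and CMR consent.* State whether assigned or actual factor values are used, and record the change from ANOVA in Section 14.
- **If it already adjusts**, keep the SAP model, make sure Section 14 records the departure from the protocol's ANOVA, and change nothing else.

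Leave KCCQ, HCMSQ and other continuous variables to the SAP's model.

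The cost is a sentence in the SAP and an entry in Section 14. No new data are needed: baseline CPET and stress echo are done at Screening, and SAP 6.3 already summarises both assigned and actual factors. With 220 participants, error degrees of freedom go from 220 − 2 = 218 to 220 − 7 = 213, moving the critical t from 1.9709 to 1.9712. The protocol can stay as an outline, so the question of an amendment under Protocol 14.4 need not arise.

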#### 12.4.8 Safety Analyses

All safety analyses will be performed on the Safety Population using the following common rules:

- The baseline value is defined as the last available value before the first administration of study drug
- For quantitative safety parameters based on central laboratory measurements, descriptive statistics will be used to summarize results and change from baseline values by visit and treatment group; resulting changes may be presented in shift tables or scattergrams
- The analysis of the safety variables will be descriptive and no hypothesis testing is planned

The safety analysis will focus on the treatment-emergent period, which is defined as the time from the first administration of study drug to the last administration of study drug + 56 days.

#### 12.4.8.1 Adverse Events

AEs will be mapped to system organ classes and preferred terms (PTs) using the Medical Dictionary for Regulatory Activities (MedDRA). AEs will be monitored during the study and the data analyzed with respect to overall incidence as well as severity and potential relationship of AEs to study medication. AEs with onset during the treatment-emergent period, or with an onset before the first dose of study medication that increases in severity or becomes serious during the treatment-emergent period, will be considered treatment-emergent.

Adverse event incidence tables will present the number and percentage of participants experiencing at least one TEAE by system organ class (SOC) (sorted by internationally agreed order), high-level group term (HLGT), high-level term (HLT) and PT in alphabetical order for each treatment group. Multiple occurrences of the same event in the same

participant will be counted only once in the tables within a treatment phase. The denominator for computation of percentages is the safety population within each treatment group.

Adverse event incidence tables will be provided by treatment group for all types of TEAEs: all TEAEs, all treatment-emergent SAEs and all TEAEs leading to permanent treatment discontinuation.

#### *Potential Drug-induced Liver Injury*

The incidence of liver-related AEs will be summarized by treatment group. The selection of PTs will be based on standardized MedDRA query hepatic disorder.

#### *Deaths*

The following deaths summaries will be generated:

- Number and percent of participants who died by study period (treatment-emergent period, on-study) summarized on the safety population by treatment received
- Death in non-randomized participants or randomized and not treated participants
- TEAE leading to death (death as an outcome on the AE eCRF page as reported by the investigator) by primary SOC, HGLT, HLT, and PT showing number and percent of participants sorted by internationally agreed order of SOC and alphabetic order of HGLT, HLT, and PT

#### *Pregnancy*

The following pregnancy summaries will be generated:

- Number of participants or partners of participants who became pregnant summarized by treatment received
- Outcomes of the pregnancies and analysis of the outcomes
- TEAE experienced during the pregnancy by primary SOC, HGLT, HLT, and PT showing the number and percent of participants sorted by internationally agreed order of SOC and alphabetic order of HGLT, HLT, and PT

#### *Overdose*

The following summaries for reports of overdose will be generated:

- Number of participants who experienced overdose summarized by treatment received
- Analysis of the cause and occurrence of the overdose

- TEAE experienced during the overdose by primary SOC, HGLT, HLT, and PT showing the number and percent of participants sorted by internationally agreed order of SOC and alphabetic order of HLT, HLT, and PT

#### 12.4.8.2 12-lead Electrocardiogram

The RR, PR, QRS, and QT intervals will be measured and read by a central laboratory. HR will be calculated as  $60 / (\text{RR} \times 1000)$  (with RR expressed in msec) and rounded to the nearest integer.

##### *Correction for Heart Rate*

Corrected QT interval (QTc) will be calculated using the manually over-read QT values. Each individual ECG QT value will be corrected for HR. The measured QT data will be corrected for HR using QTcF as per the following formulae/method (with QT, RR and QTc expressed in msec):

Fridericia's Correction:

$$QTcF = \frac{QT}{(RR/1000)^{1/3}}$$

##### *ECG Numeric Variables*

HR, PR, QRS, and QTcF will be summarized using descriptive statistics. QRS duration, manually over-read, will be used to determine which threshold criterion rules to apply for temporary discontinuation based on QTcF (eg, QRS duration  $<120$  msec or QRS duration  $\geq 120$  msec). See [Section 7.3.2](#). The change from baseline of these ECG parameters at each time point will be listed for each participant. For each time point of measurement, the changes from baseline will be summarized using descriptive statistics.

##### *Categorical Analysis*

The incidence count and percentage of participants with any postdose QTcF values of  $>500$  msec,  $>520$  msec, and  $>550$  msec will be tabulated for all participants. Participants with QTcF values  $>520$  msec will be listed with corresponding baseline values,  $\Delta QTcF$ , and baseline and treatment HR. The incidence count and percentage of participants with  $\Delta QTcF$  increase from baseline of  $>30$  msec and  $>60$  msec will be tabulated.

